## 5.2.3 Protocol Deviations

Major protocol deviations for the PP Analysis Set include:

- Subject did not meet Inclusion Criterion #2, which was: 2. Meet criteria for probable DLB (e.g. date of diagnosis of DLB missing).
- Subject met Exclusion Criteria #6, which was: 6. GDS score >8.

- Subject received incorrect study treatment for more than 6 weeks.
- Subject initiated prohibited medications used in the treatment of dementia during the 12 weeks treatment period.

Subject had poor compliance with study treatment (e.g., overall compliance is <80%).

In addition, subjects with treatment duration less than 6 weeks will be excluded from the PP Analysis Set.

The number (percentage) of subjects excluded from PP analysis will be summarized by reason for exclusion and treatment group. A listing of subjects excluded from PP analysis will be provided along with the description of reason for exclusion.

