Preliminary PK data in Study 002, healthy subjects (aged 50 to 85) who were treated with E2027 at 25 mg to 400 mg QD for 14 days showed that after the first dose on Day 1, the PK profile was similar to that seen in the first time in human single ascending dose study. Thereafter, steady state was reached by Day 12. After the final dose on Day 14, the steady state PK profile was similar to that of Day 1. E2027 was rapidly absorbed with median t_{max} ranging from 1.5 to 3.0 hours postdose. Thereafter, plasma E2027 concentrations declined until approximately 12 hours postdose and then remained relatively stable to 24 hours postdose of Day 14. At all doses there were subjects who showed secondary peaks at approximately 24 hours postdose of Day 14. From 24 hours postdose onwards, E2027 showed first order kinetics during the terminal elimination phase. Mean half-life after Day 14 was similar across doses, at ~40 hours, with no trend of increasing half-life with increasing dose. The accumulation ratios of C_{max} and $AUC_{(0-24h)}$ were generally consistent with the estimate from single-dose PK (~2.95-fold accumulation). Overall the mean C_{max} and AUC at steady state increased subproportionally with increasing doses from 25 to 400 mg, consistent with single dose PK characteristics. For a 16-fold increase in dose from 25 to 400 mg, $C_{max,ss}$ increased by 8.4 fold and $AUC_{(0-\tau)}$ increased by 7.7 fold. The ratio of CSF:plasma concentrations of E2027 at steady state was ~3.5%.

Healthy Japanese subjects administered E2027 400 mg QD for 14 days showed comparable $C_{max,ss}$ and $AUC_{(0-\tau)}$ as non-Japanese subjects. Their half-life and accumulation ratios at steady state were comparable to non-Japanese subjects administered E2027 400 mg QD. Therefore, no dose adjustment compared to non-Japanese subjects is required when E2027 is administered to Japanese subjects.

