9.7.1.6.1 PRIMARY EFFICACY ANALYSIS

E2027 is planned for use as a symptomatic treatment in subjects with DLB. The treatment effect of E2027 may be confounded by the use of rescue medications during the study. For the purposes of statistical analysis, rescue medications are defined as medications for treatment of symptoms of DLB that are prohibited or restricted (as specified in [Section 9.4.7.2](#)) and they are not used in accordance with the rules in [Section 9.4.7.2](#).

This confounding may mask the true treatment effect of E2027 in treating subjects with DLB. The treatment effect of interest will be the efficacy as measured by coprimary endpoints that

would be observed at 12 weeks without initiation or dose change of any prohibited or restricted medications as mentioned above regardless of whether or when the assigned treatment was discontinued due to adverse event, lack of efficacy or any other events related to treatment or study outcome. The target population (DLB subjects) is defined by inclusion/exclusion criteria.

There are 2 coprimary efficacy endpoints, change from baseline in the MoCA total score at 12 weeks and CIBIC-Plus scale at 12 weeks. Overall, there are 2 null hypotheses (H_0) to be tested in the primary analysis:

- H_{01} : There is no difference in the mean change from baseline in the MoCA total score at 12 weeks between E2027 and placebo.
- H_{02} : The proportional odds ratio based on CIBIC-Plus scale at 12 weeks between E2027 and placebo is equal to 1.

The corresponding 2 alternative hypotheses are that there is a difference in the mean change from baseline in MoCA total score at 12 weeks in this coprimary endpoint between E2027 and placebo and the proportional odds ratio based on CIBIC-Plus scale at 12 weeks between E2027 and placebo is not equal to 1.

The study will be considered positive if statistically significant improvement is observed in both coprimary endpoints in the E2027 treatment group.

The change from baseline of MoCA total score for E2027 compared to placebo will be analysed using the approach proposed by [Mehrotra, et al. \(2017\)](#) with slight modification based on reasons for missing. The following is a list of the missing reasons and their missing mechanisms:

- Data not observed because of dropouts due to AEs, lack of efficacy or any other events related to treatment or study outcome will be considered as missing not at random (MNAR).

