### 5.3.5 Handling of Missing Data, Drop-outs, and Outliers

#### 5.3.5.1 Efficacy

For non-EMA registration, for primary and secondary efficacy endpoints, there will be no imputation of missing value. MMRM and GLMM will be used to analyze repeated measures of continuous and ordinal data, respectively.

For EMA registration, for co-primary efficacy endpoint MoCA and all continuous secondary efficacy endpoints, there will be no imputation of missing value at individual level. The statistical estimate will be calculated based on the mean imputation method proposed by Mehrotra et al (2017). For EMA registration, the missing co-primary efficacy endpoint CIBIC-Plus and ordinal secondary efficacy endpoint will be imputed using control-based pattern imputation at subject level (Yuan 2014).

The date of change in AChEIs stable dose during treatment period, Screening and 12 weeks prior to Screening will be used in the sensitivity analysis to determine the censoring time. In case the date of change in AChEIs stable dose is missing, the missing date will be imputed similarly to missing start date of concomitant medication but replacing the First Dose Date by Last Visit Date before the change in AChEIs stable dose as reference date in the imputation. Please refer to AChEIs Stable Dose CRF page to determine the last visit date before the change in AChEIs stable dose. Where non-AChEI restricted medications are changed during the treatment period, Screening and 4 weeks prior to Screening (12 weeks prior to Screening for memantine), the above method will be used similarly.

Post-ED data will be included in all the analyses.

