#### **Supplementary Analysis for both non-EMA and EMA registrations**

Subgroup (eg, region, age group, baseline AChEI status, baseline memantine status, and baseline MMSE subgroup) analyses will be performed for the subgroups defined in Section 5.3.4. The treatment effect within each subgroup and corresponding 95% CI for each co-primary endpoint will be summarized and also depicted using forest plot.

The treatment effect will be also examined using PP Analysis Set for each co-primary endpoint and analysis.

Descriptive statistics and graphical presentation for each co-primary endpoint will be provided.

Table 4 Primary Efficacy Analyses			
Score		Analysis for non-EMA Registration	Analysis for EMA Registration
MoCA	Primary	MMRM	Control based mean imputation with Mehrotra

	Sensitivity	As primary, but censor changes in AChEI medication	As primary, but censor changes in AChEI medication
	Supplementary	As primary, subgroups	As primary, subgroups
		As primary, Per Protocol Analysis Set	As primary, Per Protocol Analysis Set
CIBIC-Plus	Primary	GLMM	Proportional odds model with control-based pattern imputation
	Sensitivity	Censor changes in both AChEI and non-AChEI medications	Censor changes in both AChEI and non-AChEI medications
		Exclude subjects with changes/new AChEI and non-AChEI restricted medications	Exclude subjects with changes/new AChEI and non-AChEI restricted medications
	Supplementary	As primary, subgroups	As primary, subgroups
		As primary, Per Protocol Analysis Set	As primary, Per Protocol Analysis Set

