#### 8.1.2 Treatment Duration for Efficacy Analyses

If additional data are collected other than scheduled visits, the additional data will be mapped to the closest scheduled visit if the data on this scheduled visit is missing.

A treatment visit is defined as occurring between the first dose and Early Discontinuation (ED) Visit (for early discontinuations) or Week 12 visit (for completers). A Post ED visit is defined as occurring after the ED Visit, more detail below.

To allow for the separate analyses where 1) all data is used and 2) only data up to and including ED visit is used, two analysis flags will be presented for efficacy analysis visits. Subjects who have a post ED visit and treatment visit in the same window will flag 1) the one closest to target date out of the two visits for all data, or 2) the treatment visit for data up to ED visit.

Windowing Period	Study Day Range (Relative to First Dose)	Week
Screening	$(-42) \leq \text{Day} \leq (-8)$	
Baseline	$(-7) \leq \text{Day} \leq (-1)$	
Analysis Baseline	-	a
Treatment	$1 \leq \text{Day} \leq 63$	6 (d)
Treatment	$64 \leq \text{Day} \leq 98$	12 (d)
Post ED	$1 \leq \text{Day} \leq 63$	6 (e)
Post ED	$64 \leq \text{Day} \leq 98$	12 (e)
End of Treatment (EOT)	-	b
Follow up	Follow up visit	c

- a: All pretreatment assessments are conducted during Screening/Baseline Periods before Day 1. The Analysis Baseline is the last non-missing value measured during pretreatment phase.
- b: For completer, EOT is the Week 12 visit. For early discontinuation, EOT is the Early Discontinuation (ED) visit. If the above visits are missing, then the last non-missing value collected not later than 7 days after the last dose will be used.
- c: If follow up visit is missing, there will be no imputed follow up visit. Unscheduled visits can be mapped to follow up for listings, but the CRF follow up visit will be used for analysis.
- d: For assessments with no Week 6 planned assessment, the window for the Week 12 assessment is  $1 \leq \text{Day} \leq 98$ . The data must be within in the date of first dose and date of ED visit (for early discontinuation subjects). For completers, date of last dose is irrelevant, window the visit based on study day range in above table.

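### The per-protocol set does not clearly exclude subjects who stop drug between Weeks 6 and 12, and their off-drug scores can serve as the per-protocol Week 12 value

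*SAP*

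**What the plan says.** **Who is in the PP set.** Planned treatment is 12 weeks. SAP 5.2.3 adds an exposure rule to its list of major deviations: "subjects with treatment duration less than 6 weeks will be excluded from the PP Analysis Set". The listed deviations are no probable DLB, GDS above 8, incorrect treatment for more than 6 weeks, starting prohibited dementia medication, and poor compliance (for example below 80%). Discontinuing drug after Week 6 is not among them.

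**Which data they contribute.** SAP 5.3.5.1 states: "Post-ED data will be included in all the analyses". SAP 5.4.1, under the supplementary analyses, states: "The treatment effect will be also examined using PP Analysis Set for each co-primary endpoint and analysis". Table 4 specifies these runs as the primary analysis in the PP set, with no exception for post-ED scores. Subjects who stop drug are expected to keep attending scheduled visits (SAP 3.2).

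**How the Week 12 value is picked.** Under SAP 8.1.2, both treatment visits and post-ED visits on Days 64-98 map to Week 12. When all data are used, the visit closest to target is taken. The same section prepares the alternative in which "only data up to and including ED visit is used, two analysis flags will be presented", but nothing links that flag to the PP analysis.

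**What kind of drug.** Protocol 9.7.1.6.1: "E2027 is planned for use as a symptomatic treatment in subjects with DLB". Protocol 7.1.1.2.1: "Mean half-life after Day 14 was similar across doses, at ~40 hours".

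**The concern.** A PP analysis is meant to describe the effect in subjects who followed the regimen. For a symptomatic drug with a half-life of about 40 hours, a cognitive or global score taken weeks after the last dose says little about the effect on drug.

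In the full analysis set (FAS), using such scores agrees with the effect defined in SAP 5.4.1, which applies regardless of discontinuation. In the PP set, the choice is inherited from a blanket sentence and no reason is given. The PP result then carries part of the same dilution as the primary analysis, so it is less useful for judging whether non-adherence explains a weak or null result.

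**Working it through.** **1. The plan's own figure.** SAP 5.2.6 caps the planned units at 84.
- One unit a day: 12 × 7 × 1 = 84.
- Two capsules once daily (Protocol 9.4.1, Table 4): 12 × 7 × 2 = 168.

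So 84 is reproduced only as dosing days. Against a literal cap of 84, a fully adherent completer would score 168/84 = 200%.

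**2. Does the 80% rule remove a fully adherent subject whose last dose is on Day 42?**

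| Denominator | Compliance | In PP set? |
|---|---|---|
| Subject's own treated period | 42/42 = 100% | Yes |
| Two capsules daily against the literal 84 | 84/84 = 100% | Yes |
| Full course | 42/84 days or 84/168 capsules = 50% | No |

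SAP 5.2.6 does not choose between these.

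**3. Time off drug if the subject is included.** The ED Visit falls within 7 days of the last dose, so by Day 49, which is in the Week 6 window. The Week 12 value then comes from Visit 8.
- Day 84: 84 − 42 = 42 days, and 42 × 24/40 = 25.2 half-lives.
- Visit window of ±3 days: 39 to 45 days.
- Day 98, the limit of the analysis window: 56 days.

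**4. Strictest reading (full-course denominator).** Passing 80% needs 0.80 × 84 = 67.2 days of dosing. The maximum time off drug is then 84 − 67.2 = 16.8 days at Day 84, or 30.8 days at Day 98.

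A concrete case has its last dose on Day 68:
- Compliance is 68/84 = 81%, so the subject is in the PP set.
- The ED Visit is by Day 75, and Visit 8 on Day 84 is 9 days later. It therefore meets the rule that post-ED visits resume more than 7 days after the ED Visit.
- Both visits fall in Days 64-98. Day 84 is on target, so it displaces the ED score.
- The Week 12 value is 84 − 68 = 16 days off drug, and 16 × 24/40 = 9.6 half-lives.

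The choice of denominator changes how long such subjects can be off drug. It does not change whether off-drug scores enter.

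**5. Size.** Let f be the share of the active PP arm scored off drug at Week 12. Assume no residual effect, so that PP difference = true difference × (1 − f). The documents give no value for f, so these shares are illustrative. The differences are those of SAP Section 4.

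| f | 1.4-point MoCA difference becomes | 0.6-point difference becomes |
|---|---|---|
| 2% | 1.37 | 0.59 |
| 5% | 1.33 | 0.57 |
| 12% | 1.23 | 0.53 |

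For scale, with SD 3 and 80 per arm the standard error of the difference is 3 × √(2/80) = 0.47. A 5% share moves the estimate by 0.05 × 1.4 = 0.07 points, or 0.07/0.47 = 0.15 standard errors.

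**The case against.** The other side has several fair points.

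- **Other exclusions apply.** A reader might infer that anyone treated for 6 weeks is admitted. The documents do not support that: five other criteria apply. On a full-course denominator the compliance rule would remove a Day 42 stopper. This stands, and it is why the 6-week figure is conditional. The word maximum in SAP 5.2.6 points towards a denominator that can shrink. So does the fact that a 6-week rule would be nearly redundant if about 67 days were already required. Neither settles it, because the duration rule would still catch short-treated subjects whose compliance is missing.
- **Analyses without off-drug data are already planned.** A reader might infer that PP is the only look at the drug taken as intended. That is not so. SAP 5.4.2 plans additional MoCA and CIBIC-Plus analyses with or without post-discontinuation data, under both the control-based and the MMRM/GLMM methods, and 8.1.3 gives by-visit summaries both ways. These name no analysis set, so by Protocol 9.7.1.6 they are FAS analyses. What remains unplanned is the combination of an adherent population with data only up to the ED Visit.
- **Six weeks is a prespecified minimum.** SAP 5.2.1 defines PP by minimal, not full, exposure, and Week 6 is the first post-baseline efficacy visit. This defends the threshold. It does not defend using post-ED scores.
- **The 12% dropout is not the relevant rate.** It describes failure to complete the study (182 randomized, 160 completing). It does not count subjects who stop drug and still attend Visit 8, so no range for f can be taken from it.

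**Conclusion.** The point holds in limited form. As written, subjects who stop drug between Weeks 6 and 12 are not clearly kept out of the PP set, and a post-ED score can be their Week 12 value. This is true on every reading of the compliance rule. Time off drug at Day 84 is at most about 16-17 days on the full-course reading and about 6 weeks on the treated-period reading.

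The effect on the estimate is likely small: about 1% shrinkage per 1% of the active PP arm affected. That rests on an assumed zero residual effect and on a share the documents do not give.

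A reader might also infer that the study's conclusion is at risk. It is not: PP is supplementary, success rests on the co-primary analyses, and using post-discontinuation data in those matches the effect SAP 5.4.1 defines. This is a cheap clarification worth making before unblinding.

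**What to change.** 1. In SAP 5.4.1 and Table 4, state that the PP analyses of MoCA and CIBIC-Plus use the existing 8.1.2 flag for data up to and including the ED Visit.
2. In SAP 5.3.5.1, except from the blanket sentence both the PP analyses and the analyses in 5.4.2 that leave out post-discontinuation data. The second exception also removes a conflict already present between those two sections.
3. In SAP 5.2.6, say whether the planned total for an early stopper is the full course or the treated period, and reconcile the cap of 84 with two capsules daily (168 over 12 weeks).
4. Leave the FAS primary analyses unchanged.

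The cost is a few sentences and a flag that is already specified. The PP analyses lose a few Week 12 values. A late stopper whose ED Visit falls on Days 64-98 keeps a Week 12 value, taken within 7 days of the last dose. An earlier stopper's Week 12 value becomes missing. In the EMA version, missing E2027 values classed as missing not at random are still imputed from placebo, so an assumed absence of effect replaces an observed off-drug score. The on-drug reading will therefore come mainly from the MMRM and GLMM versions of the PP analysis, and the report should say so.

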#### 5.2.4 Demographic and Other Baseline Characteristics

Demographic and baseline characteristics for the Safety Analysis Set, FAS and PP Analysis Set will be summarized for each treatment group using descriptive statistics, overall and by stratification factors. Continuous demographic and baseline variables include age, age at diagnosis, age at onset, years since onset of symptoms, MoCA total score, NPI total score, NPI-4 score, NPI-10 score, NPI subscores, MMSE total score, CFI score, body weight, height, disease duration, baseline UPDRS part III score, CSF cGMP, EQ-5D, EQ-5D proxy, EQ-5D VAS score, EQ-5D VAS score proxy, DEMQOL, DEMQOL proxy, SCOPA – Sleep Overall, SFQ Score, average time per day for caregiver to spend with patient, and average days per week for caregiver to spend with patient; categorical variables include age subgroup (< 65, ≥ 65 to <80, ≥ 80), sex, race, ethnicity, region, CIBIS Plus, MMSE total score subgroup (14-19, 20-26), C-CASA, C-SSRS not completed, ongoing treatment with AChEIs (yes or no), treatment with memantine (yes or no), treatment with AChEI and/or memantine (none, AChEI only, memantine only, AChEI and memantine), Hoehn & Yahr stage, relationship of caregiver to patient, caregiver reside with the patient (Yes or Not), have each clinical core feature (hallucination, fluctuation, parkinsonism, RBD) (Yes or Not), and have 2 or more core clinical feature or have only 1 clinical feature (Appendix 1 of protocol: Diagnostic Criteria for Probable Dementia With Lewy Bodies (DLB)), have each clinical supportive feature, have each indicative biomarker. Where Screening values are also collected, these may be summarized also.

Where the date of diagnosis only contains the year of diagnosis, the age of diagnosis will use the year of diagnosis – year of birth.

#### **MEDICAL HISTORY**

The medical history verbatim descriptions (investigator terms from the CRF) will be classified into standardized medical terminology using the Medical Dictionary for Regulatory Activities (MedDRA). Medical history will be coded to the MedDRA (Version 19.0 or higher) lower level term (LLT) closest to the verbatim term. The linked MedDRA preferred term (PT) and primary system organ class (SOC) will also be captured in the database.

The number (percent) of subjects will be presented by SOC and PT for each treatment group.

### 5.2.5 Prior and Concomitant Therapy

All investigator terms for medications recorded in the CRF will be coded to an 11-digit code using the World Health Organization Drug Dictionary (WHO DD). The number (percentage) of subjects who took prior and concomitant medications will be summarized on the Safety Analysis Set by treatment group, Anatomical Therapeutic Chemical (ATC), and WHO DD preferred term. Prior medications are defined as medications that stopped before the first dose of study drug. Concomitant medications are defined as medications that (1) started before the first dose of study drug and were continuing at the time of the first dose of study drug, or (2) started on or after the date of the first dose of study drug and continued up to the last dose. Prior and concomitant therapies for DLB and those for non-DLB will be summarized separately, the summaries showing therapies for DLB will also be summarized separately based on AChEI stratification.

The number (percentage) of subjects with changes in AChEI and non-AChEI restricted medications will be summarized by treatment group, Anatomical Therapeutic Chemical (ATC), and WHO DD preferred term.

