9.7.1.5 Prior and Concomitant Therapy

All investigator terms for medications recorded in the eCRF will be coded to an 11-digit code using the World Health Organization Drug Dictionary (WHO DD) (Mar 2014). The number (percentage) of subjects who took prior and concomitant medications will be summarized on the Safety Analysis Set by treatment group, Anatomical Therapeutic Chemical class, and WHO DD preferred term (PT). Prior medications will be defined as medications that stopped before the first dose of study drug. Concomitant medications will be defined as medications that (1) started before the first dose of study drug and were continuing at the time of the first dose of study drug, or (2) started on or after the date of the first dose of study drug up to the date of the last dose. All medications will be presented in subject data listings.

Medications taken within the 4-week Follow-Up Period will also be recorded.

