### **Sensitivity Analysis of the CIBIC-Plus Scale at 12 Weeks for EMA registration**

A sensitivity analysis will be produced to repeat the primary analysis for CIBIC-Plus but to censor data after changes in both AChEI and non-AChEI medications. For this the following missing mechanism will be added to the above reasons in the primary analysis

The effect had rescue medication not been made available to subjects prior to week 12 is not observable for subjects who initiated prohibited or restricted rescue medication. For these subjects, the data collected after initiation of prohibited rescue medication are assumed to contain no treatment effect in the E2027 treatment group. Technically, response data collected after initiation of new AChEIs or non-AChEIs prohibited or restricted medications (as specified in Concomitant Drug/Therapy section in the protocol) or after any change in concomitant AChEIs or non-AChEIs stable dose will be treated as MNAR such that response data treated as MNAR in the E2027 treatment group would be imputed by the mean response in the placebo treatment group as described by the imputation method below.

A sensitivity analysis that excludes all subjects with changes in AChEI or non-AChEI restricted medications will also be performed.

If the proportional odds assumption is contradicted ( $p < 0.05$  in Score Test for the Proportional Odds Assumption) by the observed data in either the entire population or any stratum, the GLMM method will be replaced by the nonparametric van Elteren test in both primary analysis and sensitivity analysis. The CIBIC-Plus scale at 12 weeks will be analyzed using van Elteren test adjusting 2 randomization stratification variables (on stabilized AChEI dose or not; geographical region [North America, Europe, Japan]). The H0 corresponding to the van Elteren test is that there is no difference in the location of distribution of the CIBIC-Plus scale at 12 weeks between E2027 and placebo. The corresponding alternative hypothesis is that there is a difference in the location of distribution of the CIBIC-Plus scale at 12 weeks between E2027 and placebo.

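### SAP 5.2.5 departs from the protocol's definition of concomitant medication, so a drug both started and stopped between first and last dose would be missing from the by-arm medication summaries

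*SAP*

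**What the plan says.** SAP 5.2.5 sorts recorded medications into two classes and summarises both on the Safety Analysis Set by treatment group, ATC class and preferred term, with DLB and non-DLB therapies shown separately.

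- Prior: "Prior medications are defined as medications that stopped before the first dose of study drug".
- Concomitant, first limb: "started before the first dose of study drug and were continuing at the time of the first dose of study drug".
- Concomitant, second limb: "started on or after the date of the first dose of study drug and continued up to the last dose".

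Protocol 9.7.1.5 has the same prior class and the same first limb. Its second limb is different: "started on or after the date of the first dose of study drug up to the date of the last dose". It adds: "All medications will be presented in subject data listings".

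SAP 5.2.5 also plans a further table: "The number (percentage) of subjects with changes in AChEI and non-AChEI restricted medications will be summarized by treatment group".

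**The concern.** The protocol's second limb is a condition on when the drug was started. The SAP's second limb adds a condition on how long it lasted. The two classes then no longer cover everything taken on treatment: a course lying wholly between the first and last study dose belongs to neither.

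If that rule is programmed, the tables that are meant to show which drugs each arm received understate use. This comes at a point where SAP Section 7 has removed censoring for changes in restricted medication from the co-primary analyses, so complete reporting of added drugs by arm is more useful to a reader than before.

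**Working it through.** No sample size, power or error rate is involved, so the main check is to apply both sets of definitions to the same dates. For illustration, take the first dose on Day 1 and the last on Day 84.

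| Drug taken | SAP 5.2.5, literal | Protocol 9.7.1.5 |
|---|---|---|
| Day -20 to Day -5 | prior | prior |
| Day -20 to Day 10 | concomitant (limb 1) | concomitant (limb 1) |
| Day 20 to Day 30 | **neither** | concomitant (limb 2) |
| Day 20, ongoing | concomitant (limb 2) | concomitant (limb 2) |
| Day 80 to Day 90 | concomitant (limb 2) | concomitant (limb 2) |

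The rules disagree in one row. The gap is any drug that starts on or after the first dose and stops before the last dose. A short course still running at either boundary is counted under both rules. The literal SAP rule also makes the classification depend on when study drug ended: the Day 20 to 30 course would count as concomitant in a subject whose last dose fell between Day 20 and Day 30, but not in a completer.

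**Is the change declared?** SAP Section 7 does not mention it, and the summaries of changes for SAP Versions 2, 3 and 4 do not list Section 5.2.5. Nothing suggests that the narrower rule was intended.

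**Which drugs fall in the gap?**

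- Protocol 9.4.7 records every medication together with the event or condition it treated. A time-limited course for an adverse event on treatment fits the gap.
- Protocol 9.4.7.2 allows permitted new medications to be started during the study.
- Protocol 9.4.7.2 also allows as-needed drugs for the lumbar puncture. The second puncture is at Week 9 (Day 63), three weeks before the planned end of treatment.

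**How large could the lumbar-puncture source be?** Protocol 9.7.2 expects about 30% of 182 randomised subjects in the CSF substudy: 182 × 0.30 = 54.6. With its three dropout rates:

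- 12%: 54.6 × 0.88 = 48.0
- 20%: 54.6 × 0.80 = 43.7
- 50%: 54.6 × 0.50 = 27.3

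These reproduce the plan's 48, 44 and 27. So, on the plan's own assumptions, at most about 48 subjects over both arms could lose a Week 9 puncture drug from the tables. The documents do not say how many would take one, so the range is 0 to 48. For courses given for adverse events there is no figure at all.

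**Which drugs are protected?** Protocol 9.4.7.2 places restrictions on cholinesterase inhibitors, memantine, Parkinson's drugs, and antipsychotics, hypnotics, anxiolytics and antidepressants. Changes in restricted drugs go into the separate table in SAP 5.2.5, which does not use the concomitant label. That table appears to include new starts: the SAP text describes one analysis as "A sensitivity analysis that excludes all subjects with changes in AChEI or non-AChEI restricted medications will also be performed", and Table 4 labels the same analysis "Exclude subjects with changes/new AChEI and non-AChEI restricted medications".

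**The case against.** The strongest case against the point is that little depends on it. The SAP phrase may be a loose paraphrase of the protocol. SAP 8.2.3 provides for a subject taking the same concomitant drug more than once, so separate courses are contemplated. The derivation rules and table shells sit in other documents (SAP Sections 9 and 11), and the program may already be right. This stands as a limit: the mismatch in the text is certain, but an actual loss of data is not.

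A reader might also infer that brief rescue use and short courses of psychotropics disappear from the tables, so that confounding is hidden. The documents do not support that. Those drugs are restricted, and changes in them are tabulated by arm in the same SAP section. Possible confounding by medication changes is addressed by dedicated analyses: censoring for MoCA and CIBIC-Plus, exclusion of affected subjects for CIBIC-Plus, and the per-protocol set. None of these uses the concomitant label.

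Part of the rescue argument remains open. Pimavanserin is prohibited rather than restricted in protocol 9.4.7.2, and it is unclear whether the restricted-medication table covers it. Even there the loss is limited. The protocol has subjects who start it discontinued. SAP 5.2.3 makes starting a prohibited dementia drug a per-protocol exclusion, reported by reason and arm.

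Finally, the protocol still lists every medication. That is true, but individual listings do not replace counts by arm.

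**Conclusion.** The definition is wrong as written, and the severity is low. SAP 5.2.5 conflicts with protocol 9.7.1.5 without saying so. If applied literally, it omits from the by-arm prior and concomitant summaries every drug both started and stopped between the first and last study dose. It does not omit every short course, because courses running at the first or last dose still count.

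The loss falls mainly on permitted, unrestricted drugs and possibly on prohibited drugs outside the restricted-medication table. Its size cannot be derived from the documents, apart from the ceiling of about 48 subjects for the lumbar-puncture source. No efficacy estimate or test is affected. The conclusion rests on two assumptions: that the program follows the SAP text, and that the restricted-medication table includes new starts as Table 4 suggests.

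**What to change.** Replace the second limb in SAP 5.2.5 with the protocol's: "started on or after the date of the first dose of study drug up to the date of the last dose", and add that the stop date does not matter. Check that the derivation program uses the start date only for this limb. While editing, state in SAP 5.2.5 that the restricted-medication table includes new starts, and say whether prohibited drugs for DLB symptoms are included.

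The cost is one phrase, one clarifying sentence and at most one program condition. No new data are needed, and no efficacy analysis changes.
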